5.3.4.1 Renal function

Urine albumin/creatinine ratio (UACR) in spot urine will be determined and calculated at the central laboratory.

The estimated glomerular filtration rate (eGFR) will be derived from serum creatinine values, age sex and race based on the CKD-EPI equation [[R12-1392](#)].

$$\text{GFR} = 141 \times \min(\text{Scr} / \kappa, 1)^\alpha \times \max(\text{Scr} / \kappa, 1)^{-1.209} \times 0.993^{\text{Age}} \times 1.018 \text{ [if female]} \times 1.159 \text{ [if black]}$$

where;

S_{cr} is serum creatinine in mg/dL,
 κ is 0.7 for females and 0.9 for males,
 α is -0.329 for females and -0.411 for males,

min indicates the minimum of S_{cr}/κ or 1, and
max indicates the maximum of S_{cr}/κ or 1.

The race of the patient will be entered because of potential differences due to race. The CKD-EPI equation considers the race as an adjustment factor, therefore the race must be known for accurate estimation.

In case of an eGFR loss of $\geq 40\%$ since baseline, or when the eGFR drops to < 15 mL/min/1.73 m² for patients with an eGFR ≥ 30 mL/min/1.73 m² at baseline (< 10 mL/min/1.73 m² for patients with an eGFR < 30 mL/min/1.73 m² at baseline), an additional visit between 30 days to preferably 60 days after detection should be scheduled (unless detected at the EOT visit at trial end) to collect a blood sample for repeat central analysis of creatinine for calculation of the eGFR. If a signal of abnormal creatinine or eGFR is reported to the trial site by others (e.g., treating physicians from local labs) an additional sample should be sent to central lab, and if it is still abnormal, another sample should be sent to central lab between 30 days and preferably 60 days.

Kidney function will be classified as described in the table below ([Table 5.3.4.1:1](#)).

Table 5.3.4.1: 1 Classification of kidney function

CKD stage	eGFR
1	≥ 90
2	60-89
3a	45-59
3b	30-44
4	15-29
5	< 15

5.3.4.2 Pregnancy testing:

Pregnancy testing (urine) will be performed in female patients of child bearing potential according to the time points indicated in the [Flow Chart](#). Pregnancy kits will be provided by the Central Laboratory. For reporting of pregnancy event refer to [Section 5.3.7.2](#).

5.3.4.3 Criteria for hypoglycaemic events:

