## 6. GENERAL ANALYSIS DEFINITIONS

### 6.1 TREATMENTS

There will be 4 basic treatment phases in this trial: screening, study treatment phase (with either empagliflozin 10mg or matching placebo), post-treatment and post-study. However, during the study treatment phase, patients are allowed to go off-treatment and subsequently re-start treatment. This may happen not at all or repeatedly for a given patient.

The purpose of the definitions below is to describe all the different study/treatment intervals, in which a patient can lie during the course of the trial. Note that the term "treatment regimen" also covers the "off-treatment" time periods.

Table 6.1: 1 Treatment regimens / study intervals

Label	Interval	Start date
Screening	Screening	Date of informed consent
Placebo/ Empagliflozin 10mg	Treatment	Date of first administration of double-blind study treatment
Off-treatment (if applicable)	During Treatment interval, but not on treatment	Date of last administration of the study medication before temporarily discontinuation + 1 day
Placebo/ Empagliflozin 10mg (if applicable)	During Treatment interval, after restart of study medication	Date study medication re-started
Post-treatment	Post-treatment	Date of last administration of study drug + 1 day
Post-study	Post-study	Date of trial completion +1 day

Details on the definition of on-treatment period for different endpoints are listed in [Table 6.1:2](#). The efficacy analyses will follow the intention-to-treat (ITT) principle in assigning patients to treatment groups, i.e. patients will be analysed as randomised.

Safety analyses will also assign patients to the treatment group as randomized.

If a patient erroneously receives the wrong trial drug, all subsequent medication packs dispensed to the patient will still be for the treatment group to which the patient was randomized. Therefore the adverse events will be analyzed as per randomized treatment, which is expected to reflect the prevailing treatment.

In the exceptional case that a patient took the wrong treatment, adverse events may occur while being on the wrong treatment. Analyses of this data are described in [Section 7.8.1.6](#).

Table 6.1: 2 Endpoint specific assignment to the on-treatment phase

Endpoint	Last day of assignment to the on-treatment phase (days after last intake of study medication)
Adverse events	7
Safety laboratory measurements, including Urine Albumin Creatinine Ratio (UACR)	3
Heart rate	1

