**6.7 BASELINE, TIME WINDOWS AND CALCULATED VISITS**

For serum creatinine and values based on upon this measurement such as eGFR, baseline will be defined as the mean of all available measurements from the screening visit until start of randomised trial medication. For all other endpoints, baseline will be defined as the last available measurement before start of randomised trial medication.

Since the protocol specifies, that all measurements are taken at visit 2 before any intake of trial medication, all measurements at the first day of drug intake are assumed to qualify as baseline assessments.

For randomised patients without any treatment intake: For serum creatinine and values based on upon this measurement such as eGFR, baseline will be defined as the mean of all available measurements from the screening visit until and including the day of randomisation. For all other endpoints, baseline will be defined as the last available measurement before or on the day of randomisation.

Measurements taken after the first intake of randomised trial medication will be considered on-treatment values if they have been obtained up to end of the parameter specific follow-up period as defined in [Table 6.7: 1](#) below and will be assigned to the randomised study drug for efficacy and safety analyses.

Measurements taken after the end of the endpoint specific follow-up period after the last intake of study drug will be considered post-treatment values.

On-treatment (for OC-OT analysis) or all post-randomisation (for OC-AD analysis) efficacy and safety measurements will be assigned to visits based on time windows around the planned visit dates. These time windows are defined based on the planned number of days after the date of first administration of study drug.

The time window for the first visit after randomisation starts on the day after the first intake of study drug. The midpoint between two on-treatment visits defines the end of a time window, with the midpoint being included in the time window of the preceding visit.

Table 6.7: 1 Time windows for post-baseline efficacy measurements scheduled for each on-treatment visit for the first 3 years

Visit number	Visit label	Planned days	Time window (actual days after baseline)	
			Start	End
Endpoints assessed at each on-site visit (e.g. creatinine / eGFR)				
2	Baseline A	1	NA	1
3	Week 4	29	2	57
4	Week 12	85	58	155
6	Week 32	225	156	295
8	Week 52	365	296	449
10	Week 76	533	450	617

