### Continuous endpoints:

The following endpoints will be evaluated by mixed models repeated measures (MMRM) as defined in the protocol.

- HbA1c change from baseline over time (OC-AD on the randomised set and OC-OT on the treated set)
- SBP, DBP change from baseline over time (OC-AD on the randomised set and OC-OT on the treated set)
- Weight change from baseline over time (OC-AD on the randomised set and OC-OT on the treated set)

- NT-pro BNP relative change from baseline over time (OC-AD on the randomised set and OC-OT on the treated set) (value will be transformed to the log scale before MMRM analysis. Estimates obtained from the model will then be back-transformed and reported on the original scale.)
- KCCQ overall summary score change from baseline at week 52 (OC-AD on the randomised set and OC-OT on the treated set) (model will include all timepoints up to week 52)
- KCCQ individual domains change from baseline at week 52 (OC-AD on the randomised set and OC-OT on the treated set) (model will include all timepoints up to week 52)
- KCCQ total symptom score change from baseline at week 52 (OC-AD on the randomised set and OC-OT on the treated set) (model will include all timepoints up to week 52)
- KCCQ based on patient-preferred outcome change from baseline at week 52 (OC-AD on the randomised set and OC-OT on the treated set) (model will include all timepoints up to week 52)
- UACR relative change from baseline over time (OC-AD on the randomised set and OC-OT on the treated set) (value will be transformed to the log scale before MMRM analysis. Estimates obtained from the model will then be back-transformed and reported on the original scale.)
- eGFR (CKD-EPI)cr change from baseline over time (OC-AD on the randomised set and OC-OT on the treated set)

As outlined in the protocol, the above endpoints will be analysed in a mixed model with repeated measures (MMRM), including age and eGFR (CKD-EPI)cr at baseline as linear covariates and visit by treatment interaction, baseline by visit interaction, geographical region, sex, baseline LVEF and status of diabetes at baseline as fixed effects. An additional factor of “week reachable” for the parameter in question, which for each patient is the theoretically reachable planned measurement based on the time of randomisation will adjust for the different planned study times.

An unstructured covariance structure will be used to model the within-patient errors.

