### **7.8.2 Laboratory data**

Standard safety tables will not include eGFR or creatinine, as those are shown separately as described in [Section 7.6](#).

For continuous safety laboratory parameters standardized and normalized values will be derived as well as the differences to baseline. The process of standardization and normalization as well as standard analyses for safety laboratory data are described in the BI guidance for the Display and Analysis of Laboratory Data [\(14\)](#). All analyses considering multiple of times upper limit of normal (ULN) will be based on original and not normalized data.

Laboratory parameters will be shown in conventional units. Where conventional units differ from SI units, analyses will be repeated on SI units in the appendix.

The analyses of laboratory data will be descriptive in nature and will be based on BI standards [see Data Management and Statistics Manual (DM&SM): Display and Analysis of Laboratory Data [\(14\)](#)].

Baseline for safety laboratory parameters will be the last available measurement before the start of randomised trial medication. Laboratory measurements taken up to 3 days after the last administration of randomised study drug will be considered as on-treatment. Default settings will be used for repeated values (using worst value).

Laboratory values will be compared to their reference ranges and frequency tables will be provided for the number of patients within and outside the reference range at baseline and the last measurement on treatment. Descriptive statistics will be provided by treatment group for baseline, last value on-treatment and for changes from baseline to last value on treatment.

Frequency tables will summarise the number of patients with potentially clinically significant abnormalities as defined for the current XLAB macro.

Only patients with at least one available on-treatment value will be included in the analysis of an individual laboratory parameter. All individual data will be presented in listings.

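### Cheap improvement, exploratory endpoints only: baseline UACR uses one spot-urine value although two are collected, so the baseline-dependent albuminuria analyses carry avoidable noise

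*SAP*

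**What the plan says.** Protocol 5.3.4.1 gives the specimen: "Urine albumin/creatinine ratio (UACR) in spot urine will be determined and calculated at the central laboratory". The protocol Flow Chart schedules UACR at Visit 1 (screening), at Visit 2 (randomisation) and at the later on-site visits.

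SAP 6.7 has two baseline rules. For serum creatinine and quantities derived from it, such as eGFR, "baseline will be defined as the mean of all available measurements from the screening visit until start of randomised trial medication". For the rest, "For all other endpoints, baseline will be defined as the last available measurement before start of randomised trial medication". UACR is built on urine values, so the second rule governs it. Protocol 7.3 carries the same pair of rules. SAP 7.8.2 repeats the last-value rule for its own domain: "Baseline for safety laboratory parameters will be the last available measurement before the start of randomised trial medication". SAP Table 6.1:2 groups UACR with the safety laboratory measurements when it assigns values to the on-treatment phase. A separate paragraph of SAP 6.7 covers patients randomised but never treated, again with averaging for creatinine and eGFR only.

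Baseline UACR is then used in SAP 7.6 in:
- the log-scale MMRM listed as "UACR relative change from baseline over time", whose terms include "visit by treatment interaction, baseline by visit interaction, geographical region, sex, baseline LVEF and status of diabetes at baseline as fixed effects";
- the analysis by baseline class (<30, 30 to 300, >300 mg/g) and the table of transitions between classes;
- the ANCOVAs of change to the last on-treatment value and to follow-up;
- the risk sets of one progression and two regression endpoints for albuminuria.

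**The concern.** A spot-urine ratio is a noisy measurement. The plan already collects a second pre-treatment value and already averages creatinine and eGFR over the same two visits. It gives no reason for treating UACR differently. UACR is neither an eligibility criterion nor a stratification factor, so its Visit 1 value is not directly truncated by selection. That sets it apart from NT-proBNP, which has a Visit 1 entry threshold, and from HbA1c, which helps define a randomisation stratum.

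Two things are at stake. Error in the baseline weakens the covariate adjustment in the MMRM and the ANCOVAs. It also places some patients in the wrong albuminuria class. A patient classed above 300 mg/g on one high reading tends to read lower next time without any true change, so part of the regression seen in the transition table and in the regression endpoints is regression to the mean.

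**Working it through.** **Inputs.** The sampling visits, baseline rules and list of uses come from the documents. The plan states no SD, reliability or power for any UACR endpoint, so there is no planned figure to reproduce. Everything numerical below rests on assumed ranges.

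**1. Baseline error.** With within-patient variance w and independent errors, one value has error variance w and the mean of two log values has w/2. The error is halved, not eliminated.

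**2. Baseline-adjusted residual variance, variance-component form.** Let b, w and d be the between-patient, within-patient and true-change variances of ln UACR, and k the number of baseline values:

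residual variance = (b + w + d) − b²/(b + w/k).

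Assumed SDs: between 1.3 to 1.6, within 0.4 to 0.8, true change 0 to 0.5.
- Largest gain (SDs 1.6, 0.4, 0): 0.311 falls to 0.238, a reduction of 23.5%.
- Smallest gain (SDs 1.3, 0.4, 0.5): 0.556 falls to 0.486, a reduction of 12.5%.
- Outside that grid, with true-change SD 1.0 (1.3, 0.4, 1.0): 1.306 falls to 1.236, about 5%. The lower end therefore depends on how far true levels drift.

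**3. The same quantity, correlation form.** Set the total variance of one log value to 1. Let r be the reliability of one value (assumed 0.6 to 0.9) and c the correlation of the true level between baseline and follow-up (assumed 0.7 to 1.0):

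one value: 1 − (cr)²; mean of two: 1 − (cr)² × 2/(1 + r).

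| r | c | one value | two values | variance | SE |
|---|---|---|---|---|---|
| 0.9 | 0.7 | 0.603 | 0.582 | −3.5% | −1.7% |
| 0.6 | 0.8 | 0.770 | 0.712 | −7.5% | −3.8% |
| 0.8 | 0.8 | 0.590 | 0.545 | −7.7% | −3.9% |
| 0.9 | 1.0 | 0.190 | 0.147 | −22.4% | −11.9% |

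The two forms together span 3.5% to 23.5%, quoted here as about 4% to 23%, or about 2% to 12% on the standard error. Both formulas describe what remains after adjustment for baseline.

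**4. Correlated errors.** If the Visit 1 and Visit 2 errors have correlation ρ, the averaged error variance is w(1 + ρ)/2. At r = c = 0.8 and ρ = 0.5 it is 0.2 × 1.5/2 = 0.15. The residual becomes 1 − 0.4096/0.95 = 0.569 against 0.590, so the gain drops from 7.7% to about 3.7%.

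**5. Classification.** Simulation on a lognormal model (median 22 mg/g, log SD 1.3 or 1.7, r 0.6 to 0.9, no true change), comparing one value with the geometric mean of two:

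| Quantity | One value | Two values |
|---|---|---|
| Wrong class (<30, 30 to 300, >300) | 11% to 27% | 8% to 20% |
| Classed >300 at baseline, one repeat ≤300 | 35% to 76% | 28% to 64% |
| Classed ≤300 at baseline, one repeat >300 | 1.0% to 4.5% | 0.9% to 4.6% |

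Class error falls by 3.2 points at one end (11.2% to 8.0%) and 7.0 at the other (26.6% to 19.6%). The third row shows why the progression endpoint gains almost nothing. The second row concerns a single repeat. Both regression endpoints require a sustained change, so it shows the direction of the effect and is not an estimate of false endpoint events. Regression to below 30 mg/g was not simulated; the same selection mechanism applies to its risk set.

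**The case against.** The strongest reply is that the last-value rule is the plan's general default, stated consistently in both documents, and creatinine/eGFR is the one exception. That exception is understandable, because eGFR underlies a key secondary endpoint, is a covariate in the primary model and, at screening, defines a stratum. UACR has none of these roles. This stands: there is no contradiction in the plan, only a cheap gain not taken.

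Visit 1 is also not a perfect replicate. It is non-fasting while Visit 2 is fasting, it may fall up to 28 days earlier, screening is exempt from the preference for morning visits, and diuretics need to be stable only for the week before Visit 2. These points have some force. However, the scheduled on-site visits from Week 4 to Week 148 are also non-fasting (the EOT and Follow Up visits are fasting), and the plan accepts averaging creatinine over the same two visits.

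The size is driven by assumption. Independent errors and two usable values per patient are both favourable assumptions: step 4 shows what correlation does, and SAP 7.6 sets UACR to missing when urine albumin is below quantification.

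A reader might infer that every albuminuria output is affected, or that the noise distorts the treatment comparison. The documents support neither. Values at each visit and the change from last on-treatment value to follow-up do not use baseline UACR. Randomisation makes the noise equal between arms in expectation.

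**Conclusion.** The point holds as a low-cost improvement to exploratory analyses. The affected outputs are the log-UACR MMRM, the two ANCOVAs, the baseline classes, the transition table and the risk sets of the two regression endpoints. The loss is one of precision and class assignment. There is no between-arm bias and no type I error consequence, and the primary and key secondary results are untouched, because UACR is outside the testing hierarchy and in none of those models.

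The gain is about 4% to 23% in baseline-adjusted residual variance, about 2% to 12% in standard error, and about 3 to 7 percentage points in class error. All three rest on assumed variances, independent errors and two quantifiable values per patient. The middle of the correlation-form grid (r = c = 0.8) gives 7.7% and 3.9%, so the upper ends should not be read as expected values.

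**What to change.** In SAP 6.7 and protocol 7.3, define baseline UACR as the geometric mean of all available values from the screening visit until the start of trial medication. For randomised but untreated patients, take values up to and including the day of randomisation. Where only one value is quantifiable, use that value. Exempt UACR from the last-value rule in SAP 7.8.2; otherwise that section would conflict with the new definition. Apply the new baseline to all the uses listed above, keep the last-value baseline as a sensitivity analysis, and leave other baselines unchanged.

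No new samples, visits or assays are needed. The cost is a few sentences in three places, some programming, and a baseline that partly reflects a non-fasting screening sample taken up to 28 days before randomisation, possibly before a diuretic change.

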### Baseline definition for concomitant therapies

Concomitant medication taken at baseline is any medication with start date 'continued' or before date of first study medication intake (randomisation date will be used for patients not treated) and end date continued on or after date of first study medication intake (randomisation date will be used for patients not treated).

### Time windows for assignment of planned off-treatment measurement

For evaluation of the off-treatment assessment 'at 30 day follow-up' only values obtained at  $\geq 23$  days to  $\leq 45$  days after last trial drug stop will be considered.

The value that is closest to the planned day of 30 days after last trial drug stop will be used. If there are 2 values equally close, the later value will be used.

## **6.8 CALCULATION OF TIME TO EVENT**

This section describes the calculation of the time to event and the time that patients without an event are in the study (under risk).

Consistent with that approach, the respective time intervals determine the start and end for the derivation of occurrence of a specific event.

For those patients with an event, the time to event is calculated as:

$$\langle \text{date of event} \rangle - \langle \text{start date} \rangle + 1$$

For those patients without an event, the time at risk is calculated as:

$$\langle \text{date of censoring} \rangle - \langle \text{start date} \rangle + 1$$

### **6.8.1 Start date**

In general, the time to event will be derived from the date of randomisation.

If study drug administration happened before calling IVRS, the date of first drug administration will be used as start date.

For the following endpoints (analysed as occurrence or time to first event), the date of first drug intake will be used as start date:

- AE analyses according to [Section 7.8.1](#)
- Endpoints purely based on laboratory measurements, that include a relation to baseline (such as change decrease from baseline  $\geq 40\%$ , doubling vs baseline, etc. )

Please note, that for composite endpoints, that include component(s) using randomisation date and other component(s) using first drug intake date as start date, the time at risk for the composite will start with date of randomisation (which may be earlier). For the individual components, the component specific start date will be used.

### **6.8.2 Date of event**

For adjudicated events, the date determined by the adjudication committee will be used; this can be different from the investigator reported date.

For the endpoints of time to CV death, time to all-cause mortality and time to non CV death the respective death date will be used rather than time to the first onset of the fatal AE.

For composite outcomes, e.g. time to adjudicated HHF or adjudicated CV death, the earliest onset date of the corresponding components will be used. For the component of CV death or other death components, date of death will always be used rather than the onset date also for composite outcomes.

For endpoints, where myocardial infarction (MI) and stroke are included as a fatal and non-fatal component, the onset of the event is considered for the derivation of time to first occurrence, not the date of death. For time to CV death the date of death is used for a fatal MI or fatal stroke.

The time to first occurrence type of endpoints based on laboratory data including endpoints including the requirement a “sustained” measurement are determined by the date of the first measurement that fulfils this condition.

For events with multiple possible episodes, such as HHF or all-cause hospitalisation, the onset date of the first episode will be used unless noted otherwise. The same applies to time-to-AE analysis.

For efficacy endpoint analyses (endpoints described in [Sections 7.4-7.6](#)):

As described in [Section 4](#), the follow-up period will not be included in the time at risk for efficacy endpoints. Therefore events later than the date of treatment discontinuation (if reason for discontinuation was completion) will not be counted.

For the primary endpoint and the key secondary endpoint of recurrent HHF, additionally there will be sensitivity analysis including all events up to individual trial completion including the FU period.

